9.4.9.1 Pulmonary Function Tests

Analysis of the spirometric data will be fully described in the SAP.

Baseline for spirometry will be defined as the mean of the 60-minute and 30-minute pre-dose values at Visit 4. On dosing days after Visit 4, these are the 60-minute and 30-minute pre-dose values. At subsequent (non-dosing) visits, morning trough FEV_1 will be defined as the mean of 2 measurements performed approximately 30 minutes apart. If one of the measurements is not available or conducted post-dose, the other value will be used as the morning trough FEV_1 .

Change from baseline in morning trough FEV₁ will be summarized descriptively by visit and by treatment group.

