## 4. INTRODUCTION

This statistical analysis plan (SAP) explains in detail the statistical analyses that will be performed for the Upstream Bio UPB-CP-01 study. The study is sponsored by Upstream Bio and being conducted in partnership with tranScrip. The analysis is outlined within the study protocol V8.0, dated 17 Jan 2023, and this SAP contains a more technical and detailed description of those analyses outlined in the protocol. In particular, information is provided on the definitions of the study populations, and it also details the list of Tables, Figures and Listings (TFL) that will be produced by S-cubed Biometrics for use and inclusion with the Clinical Study Report (CSR).

This SAP provides a detailed description of the analyses that will be undertaken at the time of each analysis and has been written and finalised before the statistical and programming teams are unblinded for the Primary (Week 24) Analysis. The Sponsor personnel are unblinded throughout the study and so their involvement in any changes to the statistical analysis specified in the SAP beyond the first draft will be documented in an appendix to the final SAP.

A Blinded Data Review Meeting (BDRM) will be conducted when the study is complete (all subjects have completed Week 32 visit) and data is cleaned, prior to final database lock.

Additionally, an unblinded administrative interim analysis will take place prior to the Primary Analysis. The outputs and analyses required for the administrative interim analysis are described in this SAP also.

Any deviations from the protocol specified analyses will be listed in [Section 11](#), and any deviations from the analyses stated within this SAP, will be described within the CSR.

Below is a summary of the protocol updates, any changes required to the statistical analysis plan (SAP) as a result of these changes have been incorporated as appropriate.

Following MHRA/REC review, Version 4.0 was created which updated the inclusion criteria and restrictions related to pregnancy and contraception, increased the frequency of symptom driven physical examinations and amended the wording around stopping criteria and restarting the trial. Version 5.0 made a number of non-substantial changes to the protocol:

- Correction to order of assessments to allow blood draws to occur earlier in the visit to minimise diurnal variations in the level of eosinophils.

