### **10.11.2. Spirometry**

FeNO and other spirometry parameters (FEV1, FEV1%, FVC and PEF) will be summarized by visit as absolute values, change from baseline and percentage change from baseline, by treatment group. Any scheduled pre-baseline data will also be summarized by visit and treatment group.

Plots of the mean over time will be displayed for each of the spirometry parameters listed above and all spirometry parameters collected will be included within subject listings.

Baseline for spirometry will be defined as the 60-minute pre-dose values at Visit 4. On all other dosing days the values recorded at 60 minutes pre-dose will be summarized. In case of multiple measurements at 60 minutes pre-dose (unexpected), the average of these will be used for baseline and the best (maximum) of these values will be used at the post-baseline timepoints. On all non-dosing post-baseline days the best (maximum) of the 2 measurements performed will be summarized.

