## **11.CHANGES TO THE PROTOCOL SPECIFIED ANALYSIS DETAILED IN THE STATISTICAL ANALYSIS PLAN**

The PK and PD Populations have been refined to clarify the need for baseline and post-baseline results for subjects to be included in either of these populations. The updates have been implemented to align the populations in terms of their requirement for post-baseline results.

It was initially planned to carry out analyses at 4 timepoints during the study: Part A – Week 24, Part A – Week 32, Part B – Week 24 and Part B – Week 32. It has since been agreed that only one formal analysis will take place, at Week 32, when all subjects (Part A and Part B) have completed the study.

During the study it was decided not to proceed with some of the exploratory cytokines. The cytokines that are available will be summarised as described in [Section 10.11.1](#).

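### SAP 10.11.2 compares a single baseline spirometry reading with the maximum of two on non-dosing days, an unlisted departure from the protocol that inflates within-group change

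*SAP*

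**What the plan says.** SAP 10.11.2 changes the statistic with the type of visit. At baseline: "Baseline for spirometry will be defined as the 60-minute pre-dose values at Visit 4". Later dosing days also use the 60-minute pre-dose value. For the remaining visits: "On all non-dosing post-baseline days the best (maximum) of the 2 measurements performed will be summarized". If several readings were taken at 60 minutes, which the SAP does not expect, "the average of these will be used for baseline and the best (maximum) of these values will be used at the post-baseline timepoints". These values feed the change, percentage-change and mean-over-time displays for FEV1, FEV1%, FVC and PEF.

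Protocol 9.4.9.1 differs: "Baseline for spirometry will be defined as the mean of the 60-minute and 30-minute pre-dose values at Visit 4". For later dosing days it names the same two pre-dose readings without saying how to combine them. At non-dosing visits, morning trough FEV1 "will be defined as the mean of 2 measurements performed approximately 30 minutes apart". It also covers a missing reading: "If one of the measurements is not available or conducted post-dose, the other value will be used as the morning trough" value.

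On disclosure, SAP Section 4 states: "Any deviations from the protocol specified analyses will be listed in" its Section 11. That section has three items: the analysis populations ("The PK and PD Populations have been refined to clarify the need for baseline and post-baseline results"), the move to one analysis at Week 32, and the cytokines that were dropped. Spirometry is absent. The SAP was written against protocol version 8.0, but the version 9.0 change list shows no change to 9.4.9.1, so the version gap does not explain the difference.

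**The concern.** Taking the best value is applied only after baseline. The maximum of two readings can never be below the first of them. So if the first reading on a non-dosing day has the same expectation as the baseline reading, the expected change without any drug effect cannot be negative, and it is positive whenever the second reading sometimes exceeds the first. This direction does not depend on normality or on the size of the measurement error.

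The artefact sits in the displayed result. Change-from-baseline tables and mean plots would show improvement in all groups, including placebo. Because later dosing days use a single reading, a cohort's curve would also step down at a dosing visit and up at the next non-dosing visit for reasons unrelated to treatment. FEV1 tables are part of the administrative interim (SAP 13.2), and protocol 9.4.8 names FEV1 for dose- and exposure-response modelling.

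**Working it through.** The plan states no SD, effect size or power for FEV1, so there is no figure of its own to reproduce.

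**1. The rules side by side**

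| | Protocol 9.4.9.1 | SAP 10.11.2 |
|---|---|---|
| Baseline (Visit 4) | mean of 60- and 30-minute readings | 60-minute reading |
| Later dosing days | both pre-dose readings named, combination not stated | 60-minute reading |
| Non-dosing days | mean of two (FEV1) | maximum of two |

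**2. Bias with no drug effect.** Let X1 and X2 be two exchangeable normal readings at a visit with within-visit SD s.

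- max(X1, X2) = (X1 + X2)/2 + |X1 − X2|/2.
- X1 − X2 has SD s√2, so E|X1 − X2| = s√2 × √(2/π) = 2s/√π.
- E[max] − E[single] = s/√π = 0.564s.

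The documents do not give s. Assumed values:

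- s = 50 mL: 28 mL
- s = 100 mL: 56 mL
- s = 150 mL: 85 mL

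Simulation with 1,000,000 draws gave the same values to the nearest mL. Mean minus mean, single minus single, and maximum minus maximum all have zero bias.

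**3. If the two readings are not exchangeable.** Let the second differ from the first by δ on average, and let θ = s√2. Then E[max] − E[first] = δΦ(δ/θ) + θφ(δ/θ). For s = 50, 100 and 150 mL:

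- δ = −50 mL: 10, 35 and 62 mL
- δ = +50 mL: 60, 85 and 112 mL

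The size moves; the sign does not.

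**4. Visits affected.** Protocol Tables 5, 6 and 8 give ten post-baseline spirometry visits: Days 8, 15, 29, 57, 85, 113, 141, 169, 197 and 225. The Table 8 spirometry row has one cell too many in the available text; the later visits were aligned with the haematology row of the same table and with Table 6.

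Dosing days are redacted and have to be inferred:

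- Cohorts 1–2, Days 29 and 57: three doses, a Dosing Period ending at Day 57 in Table 6, and extra visits on Days 28 and 56.
- Cohort 3, Day 85: footnote o to the schedule makes Week 12 a non-dosing visit for Cohort 4 only.
- Cohort 4: no dosing visit after Day 1 under protocol version 9.0.

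The inflation then applies at 8 of 10 visits in Cohorts 1–2, 9 of 10 in Cohort 3 and 10 of 10 in Cohort 4. Seven visits (Days 8, 15, 113, 141, 169, 197, 225) are non-dosing for every cohort, and there it cancels between active and placebo. With no drug effect the Cohort 1–2 curves would drop at Day 29 and rise between Day 57 and Day 85, after the last dose.

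**5. Contrasts at Days 29, 57 and 85.** A dosing cohort and a non-dosing cohort differ spuriously by 0.564s. Against pooled placebo (two subjects per cohort), the shift is the cohort's own bias minus the average bias over the pooled cohorts. Illustrations:

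- Four cohorts pooled, Days 29 and 57: the average is 0.5 × 0.564s = 0.28s, so −0.28s for Cohorts 1–2 and +0.28s for Cohorts 3–4.
- Four cohorts pooled, Day 85: the average is 0.75 × 0.564s = 0.42s, so −0.42s for Cohort 3 and +0.14s for the others. At s = 100 mL that is −42 and +14 mL.
- Part A only, Days 29 and 57: −0.19s for Cohorts 1–2 and +0.38s for Cohort 3. Day 85: +0.19s and −0.38s.

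If Cohort 4 were handled as dosed at Day 85, the four-cohort shifts there would be −0.28s for Cohorts 3–4 and +0.28s for Cohorts 1–2.

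**6. Precision.** Var(max) = s²(1 − 1/π) = 0.682s². With day-to-day SD d per visit, the SD of the change score is:

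- protocol rule: √(2d² + s²)
- maximum minus single: √(2d² + 1.682s²)
- single minus single: √(2d² + 2s²)

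At s = 100 and d = 150 mL these are 234.5, 248.6 and 255.0 mL, increases of 6.0% and 8.7%. Over s of 50–150 and d of 100–200 mL (both assumed) the increases are 1–17% and 2–24%.

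**The case against.** The strongest reply is that little depends on this. FEV1 is exploratory, nothing is tested, the sample size does not rest on it, all readings are listed by subject, and at Weeks 24 and 32 the inflation cancels against placebo. It is also modest beside the noise. With six active subjects and s = 100, d = 150 mL, the SE of the mean change is 248.6/√6 = 101 mL against a bias of 56 mL; over the assumed ranges the bias is 0.24 to 0.86 SE. All of this stands, and it limits the severity. It does not defend the rule, because a systematic shift of known direction is not excused by wide standard errors and recurs at most visits.

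The protocol leaves spirometric detail to the SAP. That is so, but 9.4.9.1 fixes these definitions itself, so the change belonged in Section 11. The departure is narrower than all spirometry: the protocol's post-baseline rule covers FEV1 only. For FEV1%, FVC and PEF the after-baseline problem is the SAP's inconsistency with itself.

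The missing-reading gap is also narrow. On a non-dosing day the maximum of one available reading is that reading, with no inflation. The gap is a missing 60-minute reading at baseline or on a later dosing day. The rule for repeated 60-minute readings should matter little, since repeats are not expected.

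The contrasts at Days 29, 57 and 85 rest on inferred dosing days, and the dosing hold noted in SAP 10.8 could change them. Pooling is not settled either: SAP 10.1.3 generally pools placebo but allows display by regimen, as does protocol 9.4.1, and by regimen the shift largely disappears. Those figures are illustrations only.

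**Conclusion.** The concern holds and should be fixed. SAP 10.11.2 applies unlike statistics before and after baseline, departs from protocol 9.4.9.1 for the baseline and for post-baseline FEV1, and does not record this in Section 11. With no drug effect, within-group change on non-dosing days is biased upward by 0.564s, or 28–85 mL for assumed s of 50–150 mL and exchangeable normal readings. The direction is secure; the size depends on s and on any systematic difference between the two readings. The harm is to within-group change and the shape of the mean curves, with possible cohort artefacts at Days 29, 57 and 85. Contrasts at common non-dosing visits and all primary and secondary conclusions are unaffected.

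**What to change.** In SAP 10.11.2, restore the protocol rule: the mean of the 60- and 30-minute pre-dose readings at Visit 4 and on later dosing days, the mean of the two readings on non-dosing days, and the single available reading where one is missing. State that the same rule applies to FEV1%, FVC and PEF. Alternatively, apply one identical statistic of the two readings at baseline and at every later visit (the maximum on both sides has zero bias) and record the change in Section 11.

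The cost is one paragraph of SAP text, one line in Section 11 if the rule differs from the protocol, and a small programming change. Both readings are already scheduled at every spirometry visit, so no new data are needed.

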**10.11.3.      *CGI-C***

The asthma clinician global impression of change (CGI-C) is a 7-point rating scale instrument used to assess the investigators evaluation of the change in asthma since baseline.

The rating scale uses the following categories:

- 1: Marked Improvement
- 2: Moderate Improvement
- 3: Minimal Improvement
- 4: No change
- 5: Minimal Worsening
- 6: Moderate Worsening
- 7: Marked Worsening

This assessment will be summarized as the number and proportion of subjects with each rating by treatment group at each visit this is collected.

A summary of the numerical score by treatment group and visit will also be displayed.

**10.11.4.      *ACQ-7***

The Asthma Control Questionnaire (ACQ-7) score is derived as an average of the responses to the 7 questions in the questionnaire. A subject is required to recall their asthma symptoms over the previous 7 days and respond, using a 7-point rating scale, to each question. The mean score is then categorised from 0 to 6, where 0 is totally controlled and 6 is severely uncontrolled.

This score will be summarized at each visit, by treatment group, along with the change from baseline in the mean ACQ-7 score.

## 10.12. Safety Analysis

The Primary endpoints for the study are safety related. All analyses of safety endpoints will be descriptive and will use the safety population. No statistical analysis of safety data will be performed.

### 10.12.1. *Injection Site Reactions*

For each injection site, information will be collected on whether any reactions are experienced by the subject. The number of subjects that ever experienced each of the reactions (pain, localised swelling, tenderness and erythema) will be summarized by treatment group, as well as the maximum severity experienced for each of the symptoms. Additionally, the number of subjects experiencing injection site reactions will be summarized by location and treatment group.

Erythema and swelling are recorded as size (in mm). The severity of these will be derived using the FDA guidance as below:

Erythema and Swelling Severity:

<2.5 cm	= None
2.5 to 5 cm	= Mild
5.1 to 10 cm	= Moderate
>10cm	= Severe.

The proportion of injections that resulted in reactions will also be summarized, by treatment group and all injection site reactions will be listed.

Any injection site reaction is also considered an adverse event of special interest and so the summaries of injection site reactions will be considered as part of the AESIs for the study.

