5.8 Safety Review Committee

5.8.1 General Safety Monitoring

Results of the SAD study performed with UPB-101 were reported in Section 1.4.1. In that clinical study, UPB-101 was safe and well-tolerated. Since the highest dose administered in the completed single-dose Phase 1 was [redacted] mg/kg (the equivalent of approximately [redacted] mg), all 3 doses proposed for Cohort 1 ([redacted]) and Cohort 2 ([redacted]) as well as the 2 doses of Cohort 3 ([redacted]) in the current study are supported by those data. However, the SRC will meet before the first subject in any cohort with [redacted] dosing receives their third dose as an extra precaution so as to assure that formal reviews of all the available safety data occur at specific timepoints in the study.

Part A: Subjects in Cohorts 1 and 2 will receive 3 doses of study drug. Before the first subject in each of those cohorts receives their third dose, the SRC will be convened. The committee will review at each of the 3 meetings the safety data available at that point in time from all enrolling cohorts. Subjects enrolled in Cohort 3 will receive 2 doses of the study drug. Therefore, no SRC meetings will be directly linked to the progress of those cohorts. The blinded safety data reviewed will include AEs, vital signs, physical examinations, ECGs, haematology, biochemistry, urinalyses, as well as subject withdrawals and replacements. Eosinophil data will not be sent to sites or reviewed by the SRC. Following this data review, the SRC will report their safety findings and make a recommendation whether the third dosing in the current cohort should proceed as planned or be modified (e.g., repeated or reduced), paused, or halted (Section 5.9 and Section 4.11).

Part B: Study drug exposures in Cohorts 4 and 5 will not exceed the exposure of any of the cohorts in Part A. If a [redacted] dosing regimen is selected for Cohorts 4 or Cohort 5 an SRC meeting will be convened prior to the first subject in the relevant cohort(s) receiving their third dose. The data to be reviewed, and the process for the SRC to report their safety findings, will be as those detailed for Part A above.

The data will be blinded for review; however, if considered necessary, the SRC can request that data be unblinded for either individual subjects or the entire dose cohort. The randomization code will be broken following tranScrip's standard procedures.

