7.2.4 Cohorts with █ Dosing Intervals

In cohorts with █ dosing intervals, study drug will be administered on Days █ for a █-week Dosing Period, except for Cohort 4 where study drug will be administered on Day 1 ONLY. None of the cohorts with █ dosing are dependent upon the SRC recommendations.

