9.4.6 Safety Analyses

All safety analyses will be conducted using the Safety Population.

MedDRA will be used to code verbatim terms of AEs. Adverse events will be summarized by system organ class, preferred term, and treatment group for the number and percent of subjects reporting AEs, the number of events, and the number of subjects with any AE. All AEs will be listed, including onset and resolution dates, verbatim term, preferred term, treatment, severity, relationship to treatment, action taken, and outcome. The pooled placebo group will be used in these summaries.

Absolute values and change from baseline physical examinations, clinical laboratory evaluations vital signs assessments, and ECG parameters will be summarized by visit and by treatment group. The frequency of subjects with safety laboratory results outside of normal reference ranges will be tabulated by treatment and visit. No inferential statistical analyses are planned for safety parameters. Placebo groups will not be pooled in these summaries.

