#### ***6.1.1. Safety Review Committee***

##### ***Part A***

Subjects in Cohorts 1 and 2 will receive 3 doses of study drug. Before the first subject in each of those cohorts receives their third dose, the Safety Review Committee (SRC) will be convened. The committee will review at each of the meetings the safety data available at that point in time from all enrolling cohorts.

Subjects enrolled in Cohort 3 will receive only 2 doses of the study drug. Therefore, no SRC meetings will be directly linked to the progress of that cohort.

The blinded safety data reviewed will include AEs, vital signs, physical examinations, ECGs, haematology, biochemistry, urinalyses, as well as subject withdrawals and replacements. Eosinophil data will not be sent to sites or reviewed by the SRC.

Following this data review, the SRC will report their safety findings and make a recommendation whether the third dosing in the current cohort should proceed as planned or be modified (e.g., repeated or reduced), paused, or halted.

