#### 10.1.3. Data Presentation

The full list of TFLs to be produced for the final study analysis are shown in [Section 13](#), and the specific format and content of each data Table/Listing presentation is shown in [Section 14](#).

Summary Tables and Figures will be presented by treatment group (and also for an Overall column including all subjects, for selected data presentations). Within all Tables and Figures values for the treatment groups will be labelled as follows:

- [REDACTED] mg [REDACTED]
- [REDACTED] mg [REDACTED]

- [REDACTED] mg [REDACTED]
- [REDACTED] mg [REDACTED]
- Placebo and/or
- Screen Failures

An Overall column may be included in the disposition, and selected safety outputs which will include all treatment groups (Active and Placebo). Generally, the placebo groups will be pooled across all cohorts however, for some summaries placebo may be summarized according to dosing regimen (e.g. Placebo [REDACTED], Placebo [REDACTED] ) or treatment group (e.g. Placebo [REDACTED]).

For screen failures, data is only expected in a selection of datasets. The data collected within these datasets will be included in the relevant listings only. Additional data that may have been collected for screen failures, in error, will not be displayed in the participants listings. They will not be included in any summary tables.

For selected outputs the dosing regimen may be used in the summaries where cohorts of the same dosing regimen (i.e. [REDACTED], [REDACTED] ) will be grouped together, similarly cohorts may be grouped together by treatment group if there are multiple cohorts with the treatment group (e.g. [REDACTED] [REDACTED]), or summaries may be produced combining all of the active groups together. The ordering of treatment groups shown here represents the order in which they will appear in outputs.

The scheduled protocol visits will be labelled in (applicable) report presentations as follows:

- Screening: Visit 1
- Screening: Visit 2
- Screening: Visit 3
- Day 1
- Day X (where X is the protocol specified Day, to be included within summary Table)
- Week X (where X is the protocol specified study Week, to be included within summary Table)

Generally, the summaries will be produced by Day, although in some cases it may be preferable to summarize by Week. This will be specified within each of the shells, as appropriate.

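### Injection-site reactions are counted per subject over the whole study and, by default, set beside placebo pooled over 3-, 2- and 1-dose cohorts, so the columns differ in opportunity to record a reaction even with no drug effect

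*SAP*

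**What the plan says.** SAP 10.12.1 gives the main tolerability summary: "The number of subjects that ever experienced each of the reactions (pain, localised swelling, tenderness and erythema) will be summarized by treatment group". It adds the maximum severity of each symptom and the number of subjects with reactions by injection location. The same section also plans a measure that allows for the number of injections: "The proportion of injections that resulted in reactions will also be summarized, by treatment group".

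On the comparator, SAP 10.1.3 says: "Generally, the placebo groups will be pooled across all cohorts however, for some summaries placebo may be summarized according to dosing regimen". No injection-site table is named there as one of the exceptions. Protocol 9.4.1 provides for placebo pooled by dosing regimen or, where appropriate, across all study parts.

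The number of doses differs by cohort:
- Cohorts 1 and 2 (Protocol 5.8.1): "Subjects in Cohorts 1 and 2 will receive 3 doses of study drug".
- Cohort 3 (SAP 6.1.1): "Subjects enrolled in Cohort 3 will receive only 2 doses of the study drug".
- Cohort 4 (Protocol 7.2.4, V9.0): "except for Cohort 4 where study drug will be administered on Day 1 ONLY".

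In the SAP table list (13.2), Table 14.3.1.1 (subject-level summary) is marked for both the final and the administrative analysis. Tables 14.3.1.2 (by location) and 14.3.1.3 (proportion with reactions) are marked for the final analysis only.

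**The concern.** A count of subjects who had a reaction at any time, and a worst severity over the study, can only rise as more doses are given. The pooled placebo column averages (3 + 3 + 2 + 1)/4 = 2.25 doses per subject, a dose count that no active cohort shares. Part of any difference between an active column and the placebo column then reflects the number of doses and not the product.

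Safety and tolerability are the primary objective, and Protocol 1.6 says the study should help to establish the dose and dosing frequency for Phase 2. Readers will compare regimens from these columns. A larger sample would not remove the difference, because it lies in the expected values.

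**Working it through.** **Inputs.** Doses per subject k = 3, 3, 2, 1 for Cohorts 1 to 4 (places given above). Each cohort has 6 active and 2 placebo subjects (SAP 6.1), so pooled placebo is 8 over four cohorts. The documents give no reaction rate and no target figure, so there is no figure of the plan's own to reproduce. Protocol 1.7 reports no injection-site reactions after the single SC dose in the earlier study. I assume a risk per dose p of 1% to 30%, equal for drug and placebo and independent between doses.

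**Formula.** P(ever) = 1 − (1 − p)^k. Pooled placebo = the mean of the four cohort values, since each contributes 2 subjects.

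At p = 10%: 1 dose 10.0%; 2 doses 1 − 0.9² = 19.0%; 3 doses 1 − 0.9³ = 27.1%. Pooled placebo = (27.1 + 27.1 + 19.0 + 10.0)/4 = 20.8%.

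| p per dose | 1 dose | 2 doses | 3 doses | Pooled placebo | 1-dose ratio | 3-dose ratio |
|---|---|---|---|---|---|---|
| 1% | 1.0% | 2.0% | 3.0% | 2.2% | 0.45 | 1.33 |
| 5% | 5.0% | 9.8% | 14.3% | 10.8% | 0.46 | 1.32 |
| 10% | 10.0% | 19.0% | 27.1% | 20.8% | 0.48 | 1.30 |
| 20% | 20.0% | 36.0% | 48.8% | 38.4% | 0.52 | 1.27 |
| 30% | 30.0% | 51.0% | 65.7% | 53.1% | 0.56 | 1.24 |

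**How far this depends on the assumptions.**
- *Within-subject correlation* (beta-binomial, p = 10%): correlation 0.3 gives ratios of 0.59 and 1.23; 0.8 gives 0.84 and 1.08.
- *Dosing hold* (SAP 10.8; doses lost not stated): if Cohorts 1 and 2 each lost one dose, the ratios over p = 1% to 30% are 0.57 to 0.66 for Cohort 4 and 1.14 to 1.11 for Cohorts 1 and 2.
- *Optional Cohort 5* with 1 to 3 doses: 0.42 to 0.62 (1 dose) and 1.18 to 1.50 (3 doses).
- *Part A alone* (3, 3, 2 doses): 0.75 to 0.84 for the 2-dose cohort and 1.12 to 1.08 for the 3-dose cohorts.
- *Injections per visit.* Protocol 1.7 gives two for Cohort 1; the other counts are redacted. With risk per injection of 2% to 20% and 1 to 4 injections per visit in Cohorts 2 to 4, the ratio to pooled placebo is 0.16 to 1.09 for Cohort 4, 0.82 to 1.96 for Cohort 1 and 0.59 to 2.21 for Cohort 2. The sign can change. For example, with total injections of 6, 3, 2 and 4 and 10% risk per injection, the rates are 46.9%, 27.1%, 19.0% and 34.4%, with mean 31.8%. Cohort 4 is then at 34.4/31.8 = 1.08.

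**In subjects.** At p = 10% per dose, independent, the expected counts are 0.6 of 6 in Cohort 4 and about 1.7 of 8 on placebo. The observed Cohort 4 rate falls below placebo in 66% of trials and above it in 26%.

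**After restriction to the first dose.** k = 1 everywhere, so at equal risk per dose every ratio is 1.00. Unequal injections per visit still matter. With 2, 1, 1 and 4 injections at 10% each, the first-dose rates are 19.0%, 10.0%, 10.0% and 34.4%, with mean 18.3%, so Cohort 4 would sit at 1.87 times pooled placebo. The first-dose table therefore needs the injection count and the per-injection proportion beside it.

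**The case against.** The strongest reply is that the plan already handles much of this. The per-injection proportion removes the effect of injection number if the risk per injection is constant. Doses and injections received are tabulated (Table 14.1.5), and all reactions are listed. Regimen-specific placebo is permitted, and Protocol 9.4.1 names it first. The column layout belongs in the SAP Section 14 shells, which are not in the reviewed copy. Everything is descriptive, and the gap at p = 10% is about 0.65 of a subject among 6 (10.8 points × 6). The SAP also rests on an earlier protocol: "The analysis is outlined within the study protocol V8.0, dated 17 Jan 2023". The single-dose Cohort 4 came with V9.0.

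Much of this stands, and it limits the claim. Four stronger readings are tempting but not supported:
- *That the single-dose cohort will show half the placebo rate.* The size, and even the direction, depends on redacted and unstated quantities.
- *That all injection-site reporting is affected.* The per-injection table is not affected in this way.
- *That the SAP commits these tables to pooled placebo.* It sets a default, and the shells may override it. The Protocol 9.4.6 sentence, "The pooled placebo group will be used in these summaries", closes the paragraph on coded adverse events and does not address the solicited reaction table.
- *That the special-interest event tables and the table of events leading to discontinuation of study drug carry the same fault.* SAP 10.12.2 describes its presentations as covering unsolicited events, so it is unclear that solicited reactions are counted again there. The discontinuation denominators belong in the unseen shells.

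The reply does not remove the core point. The per-injection table leaves the subject-level, maximum-severity and by-location rows unadjusted, and it is not planned for the administrative analysis, where 14.3.1.1 appears without it. The 3-versus-2-dose mismatch exists in Part A whichever protocol version applies.

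**Conclusion.** The point holds as a comparability weakness in Tables 14.3.1.1 and 14.3.1.2, conditional on the default placebo pooling being applied there. The base-case ratios (0.45 to 0.56 for one dose, 1.24 to 1.33 for three) assume all planned doses given, four cohorts, and equal, independent risk per dose of 1% to 30%. They illustrate the mechanism and do not predict the result. Correlation and lost doses pull the ratios towards 1, while unequal injections per visit can widen or reverse them. A reader cannot correct for this by eye, so a matched display is worth specifying, although the expected differences amount to a fraction of a subject to one or two subjects per cohort.

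**What to change.** In SAP 10.12.1 and the table list:

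1. Add a first-dose summary using the D1, D2, D4 and D8 checks, which Protocol Table 5 schedules for every cohort. Make it the comparison of each active group with pooled placebo, and show the number of injections given at that visit and the per-injection proportion.
2. For the whole-study 'ever' and maximum-severity rows, show placebo by dosing regimen alongside the pooled column, as SAP 10.1.3 and Protocol 9.4.1 already allow.
3. Produce the per-injection table (14.3.1.3) wherever 14.3.1.1 is produced, including the administrative analysis.

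The cost is SAP wording and one extra table layout, with no new data. The downside is that regimen-specific placebo columns hold only 4 subjects (3 doses), 2 (2 doses) and 2 (1 dose), which is why the first-dose table keeps the full pool of 8.
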